#### 3.2 Secondary Objectives

The following objectives will compare full, medium and low dose subjects in the blinded portion of Stage 1:

- Assess changes in posttraumatic growth via Post Traumatic Growth Inventory (PTGI) scores from baseline to the primary endpoint.
- Assess changes in global functioning via Global Assessment of Functioning (GAF) scores from baseline to the primary endpoint.
- Assess changes in symptoms of depression via Beck Depression Inventory-II (BDI-II) scores from baseline to the primary endpoint.
- Assess changes in self-reported sleep quality via the Pittsburgh Sleep Quality Index (PSQI) from baseline to the primary endpoint.
- Assess self-reported dissociation symptoms with the Dissociative Experiences Scale-II (DES-II) from baseline to the primary endpoint.
- Assess changes in Neuroticism-Extroversion-Openness Personality Inventory (NEO PI) scores from baseline to the primary endpoint.

The following objectives will include exploratory analyses intended to inform protocol design:

- Explore the effects of each MDMA-assisted psychotherapy session upon self-reported changes in consciousness, as those associated with a transformational or mystical experience via the States of Consciousness Questionnaire (SOCQ).
- Assess the effects of a third active dose experimental session by comparing Global CAPS, BDI-II, GAF, PSQI, PTGI (in reference to start of the study), and DES-II scores at the primary/secondary endpoint and end of Stage 1/ Stage 2 in subjects receiving a third experimental session in Stage 1 and Stage 2.
- Assess the ability of the investigators and subjects to accurately guess condition assignment when asked to do so after each blinded experimental session.
- Assess value of third experimental session in Stage 1/Stage 2 by collecting each active dose subject's perception of experimental sessions at the primary/secondary endpoint and end of Stage 1/ Stage 2.
- Correlate adherence to the Treatment Manual with Global CAPS scores using adherence criteria ratings to assess videos of psychotherapy sessions.
- Assess PTSD symptoms via CAPS, posttraumatic growth via PTGI, depression symptoms via BDI-II, global functioning via GAF, sleep quality via PSQI, dissociation symptoms via DES-II, and personality via NEO PI throughout Stage 2 in comparison to Stage 1 in crossover subjects.
- Assess long-term effects of receiving active dose MDMA on PTSD symptoms via CAPS, posttraumatic growth via PTGI, personality changes via NEO PI, depression

symptoms via BDI-II, global functioning via GAF, and sleep quality via PSQI one year after the final experimental session for each subject.

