When each subject completes the evaluation at the primary endpoint, the blind will be broken for that subject. Subjects who had been assigned to receive low dose or medium dose MDMA will subsequently have the opportunity to enroll in the open-label study arm, or “Stage 2.” Stage 2 must start within a maximum of 5 months after the subject finishes Stage 1. The open-label study arm will follow a similar sequence of events and procedures, except that there will be a single preparatory session, and all three MDMA-assisted psychotherapy sessions will be open-label. Subjects will receive an initial dose of 100 mg MDMA in the first experimental session, and one of two active doses of MDMA that are clinically titrated by the CI during the second and third open-label experimental sessions that will otherwise follow the same sequence of events (See Time and Events Table). Outcome measures except for the NEO PI will be repeated one month after the second Stage 2 experimental session, and all outcome measures will be repeated at the end of Stage 2.

The study will conclude with a one-year follow-up occurring 12 months after the final experimental session of Stage 1 for subjects who received full dose MDMA or who elected not to enroll in Stage 2 after receiving either the medium or low doses in Stage 1. Subjects who enrolled in Stage 2 will have their final follow-up 12 months after the final open-label experimental session. Outcome measures will be repeated at the 12-month follow-up, as well as a questionnaire concerning self-reported long-term effects of study participation.

Sub-studies in a select group of subjects in this study may be conducted for exploratory purposes. Subjects will complete a separate consent process if they chose to participate in these studies.

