## **5.0 Randomization and Blinding**

This is a randomized, triple-blind, dose response study with an open-label cross-over segment. For Stage 1, a randomization list will be prepared at the beginning of the study. If needed, subsequent randomization lists will be created to replace subjects who withdraw from the study to ensure that replacement subjects are not added to the end of the initial list. Each subject will be assigned to one of the three dose conditions; 30 mg (low dose), 75 mg (medium dose) or 125 mg (full dose). Twelve evaluable subjects will be assigned to the full dose condition, six evaluable subjects to the 75 mg condition and six evaluable subjects to the 30 mg low dose condition. The study will employ a blinded randomization procedure that will maintain the 2:1:1 ratio while maintaining the blind and ensuring that each subsequent condition assignment is not predicated on the previous assignment.

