## 8.1 Analysis Populations

*Intent-to-treat (ITT)*: all subjects who were randomized

*Per protocol (PP)*: all subjects who completed Stage 1, underwent assessment of PTSD symptoms, and did not experience a major protocol deviation

*Crossover*: all subjects who completed Stage 2 in addition to completing Stage 1

*Safety*: all subjects who receive any study treatment

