### **8.9.2.2 Secondary Efficacy Analyses at Secondary Endpoints**

#### Assess 3 vs. 2 experimental MDMA sessions

For the CAPS, PTGI, BDI-II, GAF, PSQI, DES-II, and NEO PI, the absolute changes in the measures from the primary endpoint to end of Stage 1 for the 125 mg group will be compared with t-tests. In the crossover subjects (30 mg and 75 mg group) the absolute

changes in the measures from the secondary endpoint to end of Stage 2 will be compared with t-tests.

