#### Crossover Subject Analyses

Data from subjects assigned to the low and medium dose groups, i.e. ‘crossover population,’ will be analyzed by within-subject t-tests comparing difference scores from primary endpoint in Stage 1 to secondary endpoint in Stage 2 (Table 3 and 4). The following measures total scores will be analyzed in this fashion: CAPS, PTGI, BDI-II, GAF, PSQI, DES-II, and NEO PI.

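### The crossover t-tests appear to pool subjects from 30 mg and 75 mg with no Stage 1 arm term: the estimate blends two dose steps, though power suffers materially only if the arms differ by about 1 SD or more

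*SAP*

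**What the plan says.** SAP 3.2 states the objective, to assess the outcome measures "throughout Stage 2 in comparison to Stage 1 in crossover subjects", and lists it among the exploratory aims. It names no test.

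The test is in SAP 8.9.2.2, Crossover Subject Analyses. "Data from subjects assigned to the low and medium dose groups" are named together as the crossover population and "will be analyzed by within-subject t-tests comparing difference scores from primary endpoint in Stage 1 to secondary endpoint in Stage 2". Seven instruments are listed, so there is at least one test per instrument. No Stage 1 arm factor, by-arm test or between-arm comparison is given.

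SAP 8.1 defines the Crossover population as "all subjects who completed Stage 2 in addition to completing Stage 1", without reference to arm. For the third-session comparison, SAP 8.9.2.2 again takes the arms together: "In the crossover subjects (30 mg and 75 mg group".

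SAP 5.0 assigns "six evaluable subjects to the 75 mg condition and six evaluable subjects to the 30 mg low dose condition". Under SAP 4.0, low- and medium-dose subjects "will subsequently have the opportunity to enroll in the open-label study arm", so 12 is a maximum. All who cross over receive 100 mg first and then one of two active doses. SAP 8.9 promises descriptive statistics by treatment group for every endpoint.

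**The concern.** Stage 1 dose was randomised. A subject from the 30 mg arm and one from the 75 mg arm take different steps into the same Stage 2 regimen. They also start from Visit 13 scores that already carry whatever their Stage 1 dose did. The mean of all crossover changes estimates neither step. If the 75 mg subjects had already improved and had little left to gain, the pooled mean would understate the change in one group and overstate it in the other.

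There is also a cost in precision. A one-sample t-test on the combined changes treats a systematic difference between the arms as random scatter. Both matter because SAP 6.0 gives effect-size estimation as the purpose of the pilot, and protocol 12.1 wants those estimates for a dose-response model.

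**Working it through.** **The plan's own figure.** There is none to reproduce. SAP 6.0 gives no effect size, SD or power, and protocol 12.1 says the literature has no effect-size estimate for the low and medium doses.

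**Inputs.** From the documents: 6 + 6 subjects at most (SAP 5.0) and two-sided alpha 0.05 (SAP 8.0). Assumed: within-arm SD of the CAPS change σ = 20, equal in both arms; average change -15; difference between the arm means D from 0 to 30.

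**Pooled test.** t = mean / (s_P / √12), with 11 df. Each arm mean lies D/2 from the overall mean, which adds 12 × (D/2)² = 3D² to the sum of squares. Hence E(s_P²) = σ² + 3D²/11.

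**Arm-adjusted test of the same mean.** t = mean / (s_W / √12), with 10 df and E(s_W²) = σ² whatever D is. The noncentrality is 15 / (20/√12) = 2.60, and the exact power is 65%.

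Pooled power comes from simulation with 400,000 replicates per row:

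| Mean change, from 30 mg / from 75 mg | D in SD | √E(s_P²) | Pooled | Arm-adjusted |
|---|---|---|---|---|
| -15 / -15 | 0 | 20.0 | 66% | 65% |
| -18 / -12 | 0.3 | √(400 + 9.8) = 20.2 | 65% | 65% |
| -20 / -10 | 0.5 | √(400 + 27.3) = 20.7 | 63% | 65% |
| -25 / -5 | 1.0 | √(400 + 109.1) = 22.6 | 56% | 65% |
| -30 / 0 | 1.5 | √(400 + 245.5) = 25.4 | 45% | 65% |

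A second set, in SD units with an average change of 0.8 SD, shows the same pattern. Pooled power is 71%, 71%, 69%, 62%, 51% and 38% at arm differences of 0, 0.25, 0.5, 1.0, 1.5 and 2.0 SD, against 70-71% throughout with arm in the model.

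**Fewer crossovers.** At an average of 0.8 SD and an arm difference of 1.0 SD, pooled v adjusted power is 51.5% v 60.3% with 5 per arm and 39.6% v 47.7% with 4 per arm. With equal arms the adjustment costs 1.3 points at 5 per arm (61.5% v 60.2%) and 2.0 points at 4 per arm (49.7% v 47.7%).

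**Separate tests by arm.** With equal changes of 0.8 SD, power falls from 71% pooled to 36% in each arm of 6. Two unadjusted tests have a familywise error of 1 - 0.95² = 9.75%. At (-30, 0) the 30 mg group alone has 83% power as a 6-subject t-test (5 df), or 91% if it borrows the residual variance of both arms (10 df).

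**Precision of by-arm estimates.** With an observed SD of 20 and t(10 df) = 2.228, the 95% half-width is 2.228 × 20/√6 = 18.2 points for one arm's mean change. For the difference between arms it is 2.228 × 20 × √(1/6 + 1/6) = 25.7 points.

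**The case against.** Much of the case on the other side stands.

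- Pooling is inferred. The SAP never says the arms are combined, and the plural in "will be analyzed by within-subject t-tests comparing difference scores from primary endpoint in Stage 1 to secondary endpoint in Stage 2" could cover tests by arm, although the list of seven instruments explains it equally well. The third-session sentence is looser still. It could even mean comparing the two groups with each other.
- Averaging over prior dose is a legitimate answer to a question about Stage 2 against Stage 1 in all crossover subjects.
- By-arm descriptive statistics are planned. If they cover the change scores, a reader could derive the by-arm intervals, and even the adjusted test, from n, mean and SD. They do not settle which analysis is prespecified.
- The contrast is open-label, uncontrolled and titrated. Its changes mix dose step with further sessions, time and unblinding, and an arm term does not turn them into clean dose-step effects.
- For the third-session contrast both arms are already on the Stage 2 regimen. There the arms differ in Stage 1 history rather than in the current dose step, so the case for an arm term is weaker.

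A reader might infer that pooling loses power whenever the arms differ. The calculations do not support that: up to about 0.3 SD there is no real loss, and with equal arms the pooled test is slightly better. A reader might also infer that the arms should be tested separately. With 6 per arm, that usually costs far more power than pooling does.

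**Conclusion.** The point holds as a matter of interpretation and, conditionally, of efficiency. On the natural reading of SAP 8.9.2.2, the crossover t-tests average two dose steps without accounting for the randomised Stage 1 arm.

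The power lost against an arm-adjusted test of the same average is about 2 points at an arm difference of 0.5 SD, 9 points at 1.0 SD and 20 points at 1.5 SD. These figures assume normal changes, equal SDs of 20, an average change of -15 and 6 per arm. The last two cases suppose that one arm gains very little or nothing, and nothing in the documents says this will happen. They show what is possible, not what is expected.

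The matter is confined to an open-label contrast that SAP 3.2 calls exploratory. The randomised Stage 1 comparison is untouched. It merits a wording change because the remedy is nearly free.

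**What to change.** In SAP 8.9.2.2, Crossover Subject Analyses, model each change score with Stage 1 arm (30 or 75 mg) as a factor. Test the average change using the within-arm residual variance, and state how the arms are weighted if unequal numbers cross over. Report the mean change with a 95% confidence interval in each Stage 1 arm, and the between-arm difference with its interval. Label these as descriptive estimates, not as additional significance tests. Say that they are not dose-step effects free of time, extra sessions and unblinding.

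Do the same for the Stage 2 third-session contrast, and state there that the comparison is within subject. If by-arm analysis was intended all along, the same text makes that plain.

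No new data are needed. The price is one error degree of freedom (11 to 10). That is about 1 point of power with 6 per arm and about 2 points with 4 per arm, if the arms do not differ. The by-arm intervals will be wide, about ±18 CAPS points at 6 per arm and SD 20, and wider with fewer subjects.

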### 3.3 Safety Objectives

- Suicidality will be assessed with the Columbia Suicide Severity Rating Scale (C-SSRS) before, during and after experimental sessions and on selected days of telephone or face-to-face contact, with comparisons made between subjects in each condition.
- Subjective Units of Distress (SUD) and vital signs (blood pressure, heart rate and temperature) will be measured during each experimental session, and comparisons will be made for vital signs between conditions.
- Collect changes to pre-existing tinnitus and/or chronic pain symptoms using a visual analog scale, specifically in subjects with a medical history of tinnitus and/or chronic pain.
- Serious adverse events, adverse events and spontaneously reported reactions will be collected during the study according to Section 8.3

### 4.0 Study Design

This randomized, triple-blind study will examine the safety and efficacy of MDMA-assisted psychotherapy with 30, 75 or 125 mg MDMA in twenty-four veterans, firefighters and police officers diagnosed with chronic, treatment-resistant PTSD arising from their service. These subjects will ideally, but not necessarily, include twelve men and twelve women. Supplemental doses of half the initial dose may be administered between 1.5 and 2.5 hours after the initial dose was administered.

Prior to undergoing the first MDMA-assisted (experimental) session, all subjects will undergo three 90-minute preparatory non-drug psychotherapy sessions with a male and female co-therapist team. Stage 1 of the study will consist of two blinded experimental sessions and, for the full dose group, one open-label experimental session, each lasting six to eight hours and scheduled three to five weeks apart. Experimental sessions will follow a similar sequence of events. (See Time and Events Table). A co-therapist team will perform all non-drug and MDMA-assisted psychotherapy sessions in their outpatient office. Subjects will complete the SOCQ, a measure of alterations in consciousness related to mystical experiences, during the period of time between the end of each MDMA-assisted psychotherapy session and before they leave the treatment facility the next day. Subjects will remain at the study site overnight accompanied by an attendant. Subjects will undergo three integrative psychotherapy sessions after each experimental session, with the first integrative session occurring on the day after the experimental session. All psychotherapy sessions may be recorded to audio and video.

A blinded independent rater, who will not be present during any psychotherapy sessions, will assess subject PTSD symptoms with CAPS, symptoms of depression with BDI-II, posttraumatic growth with PTGI, global functioning with GAF, sleep quality with PSQI, and dissociation with the DES-II. Changes in personality traits will be assessed via NEO-PI. Outcome assessments will be done at baseline, at the primary endpoint one month after the second experimental session, two months after the third open-label experimental session and at the 12-month follow-up and at equivalent points in Stage 2.

When each subject completes the evaluation at the primary endpoint, the blind will be broken for that subject. Subjects who had been assigned to receive low dose or medium dose MDMA will subsequently have the opportunity to enroll in the open-label study arm, or “Stage 2.” Stage 2 must start within a maximum of 5 months after the subject finishes Stage 1. The open-label study arm will follow a similar sequence of events and procedures, except that there will be a single preparatory session, and all three MDMA-assisted psychotherapy sessions will be open-label. Subjects will receive an initial dose of 100 mg MDMA in the first experimental session, and one of two active doses of MDMA that are clinically titrated by the CI during the second and third open-label experimental sessions that will otherwise follow the same sequence of events (See Time and Events Table). Outcome measures except for the NEO PI will be repeated one month after the second Stage 2 experimental session, and all outcome measures will be repeated at the end of Stage 2.

The study will conclude with a one-year follow-up occurring 12 months after the final experimental session of Stage 1 for subjects who received full dose MDMA or who elected not to enroll in Stage 2 after receiving either the medium or low doses in Stage 1. Subjects who enrolled in Stage 2 will have their final follow-up 12 months after the final open-label experimental session. Outcome measures will be repeated at the 12-month follow-up, as well as a questionnaire concerning self-reported long-term effects of study participation.

Sub-studies in a select group of subjects in this study may be conducted for exploratory purposes. Subjects will complete a separate consent process if they chose to participate in these studies.

**Table 4.0-1: Stage 1 Blinded Drug Doses**

| Condition   | Number of Subjects | Initial Dose | Supplemental Dose | Min-Max Cumulative Dose |
|--------------------|---------------------------|---------------------|--------------------------|--------------------------------|
| Low Dose    | 6                         | 30 mg               | 15 mg                    | 30-45 mg                       |
| Medium Dose | 6                         | 75 mg               | 37.5 mg                  | 75-112.5 mg                    |
| Full Dose   | 12                        | 125 mg              | 62.5                     | 125-187.5 mg                   |

**Table 4.0-2: Stage 2 Drug Doses**

| Experimental Session | Dose               | Initial Dose | Optional Supplemental Dose | Min-Max Cumulative Dose | Min-Max Cumulative Dose with Titration |
|-----------------------------|---------------------------|---------------------|-----------------------------------|--------------------------------|---|
| 1                           | Active Dose               | 100 mg              | 50 mg                             | 100-150 mg                     |   |
| 2 and 3                     | Active Dose               | 100 mg              | 50 mg                             | 100-150 mg                     |   |
|                             | + Optional Titration Dose | 25 mg               | 12.5 mg                           |                                | 125-187.5 mg                                  |

For further details please refer to the protocol Section 5.0 Protocol.

| Table 4.1: Stage 1 Time & Events           | Screen/Baseline                                 |            | Preparatory              | Experimental Session 1 |                        | Experimental Session 2 |                         |                  | Experimental Session 3         |                            | Follow-Up  |
|--|---|------------|--------------------------|------------------------|------------------------|------------------------|-------------------------|------------------|--------------------------------|----------------------------|--|
|  | Pre-Study                                       | V1         | V 2,3,4                  | V5                     | V 6,7,8                | V9                     | V 10,11,12              | V13              | V14                            | V 15,16,17                 | V18  |
| Visit #                                    |   |            |                          |                        |                        |                        |                         |                  |                                |                            |  |
| Type of Visit                              | Screening may take place over more than one day | Enrollment | Preparatory Sessions     | Experimental Session 1 | Integrative Sessions   | Experimental Session 2 | Integrative Sessions    | Primary Endpoint | Experimental Session 3         | Integrative Sessions       | End of Stage 1 & Outcome                             |
| Visit Timing or Study day or Window        | Up to 2 months prior to Visit 1                 |            | Prior to V5 M | Up to 7 weeks post V1  | Before V9 A | 3-5 weeks post V5      | Before V13 A | 1 month post V9  | 3-5 weeks post V9 N | Before V18 A, N | May happen over > 1 day. 2 mo. post V14 N |
| Initial Phone Screen                       | X   |            |                          |                        |                        |                        |                         |                  |                                |                            |  |
| Informed Consent                           | X   |            |                          |                        |                        |                        |                         |                  |                                |                            |  |
| Medical/Psychiatric History                | X   |            |                          |                        |                        |                        |                         |                  |                                |                            |  |
| General Phys. Exam (BP, Heart rate, Temp)  | X   |            |                          |                        |                        |                        |                         |                  |                                |                            |  |
| Brief Neurological Exam                    | X   |            |                          |                        |                        |                        |                         |                  |                                |                            |  |
| ECG  | X   |            |                          |                        |                        |                        |                         |                  |                                |                            |  |
| SCID-I-RV                                  | X   |            |                          |                        |                        |                        |                         |                  |                                |                            |  |
| Clinical Lab Tests, w/ HIV, HCV test       | X   |            |                          |                        |                        |                        |                         |                  |                                |                            |  |
| Collect Concomitant Medication             | X   | X          | X                        | X                      | X                      | X                      | X                       | X                | X                              | X                          | X  |
| Medication Taper (if applicable)           | X   | X          |                          |                        |                        |                        |                         |                  |                                |                            |  |
| Study Enrollment after meeting I/E         |   | X          |                          |                        |                        |                        |                         |                  |                                |                            |  |
| Record to Audio/Video                      | X L                                  |            | X                        | X                      | X                      | X                      | X                       | X L   | X                              | X                          | X L                                       |
| General Well-Being                         |   | X          | X                        | X                      | X                      | X                      | X                       |                  | X                              | X                          |  |
| Drug Screen                                | X   |            |                          | X                      |                        | X                      |                         |                  | X                              |                            |  |
| Pregnancy Screen (if applicable)           | X   |            |                          | X                      |                        | X                      |                         |                  | X                              |                            |  |
| Complete Randomization Procedure           |   |            |                          | X B         |                        |                        |                         |                  |                                |                            |  |
| CAPS, GAF, BDI-II, PTGI, PSQI, DES-II (IR) | X   |            |                          |                        |                        |                        |                         | X                |                                |                            | X  |
| NEO PI (Ind. Rater)                        | X   |            |                          |                        |                        |                        |                         | X                |                                |                            |  |
| C-SSRS                                     |   | X          | X                        | X C, D, E   | X I         | X C, D, E   | X I          | X                | X C, D, E           | X I             | X  |
| Administer IP Drug + Therapy, SOCQ         |   |            |                          | X                      |                        | X                      |                         |                  | X                              |                            |  |
| Monitoring of BP, Heart rate and Temp.     |   |            |                          | X                      |                        | X                      |                         |                  | X                              |                            |  |
| SUD  |   |            |                          | X F, E      |                        | X F, E      |                         |                  | X F, E              |                            |  |
| Beliefs of Condition Assignment            |   |            |                          |                        | X K         |                        | X K          |                  |                                | X K             |  |

|   |                |   |                  |                  |                  |                  |                  |                |                  |                  |                |
|---|----------------|---|------------------|------------------|------------------|------------------|------------------|----------------|------------------|------------------|----------------|
| Overnight Stay                          |                |   |                  | X                |                  | X                |                  |                | X                |                  |                |
| Integrative Therapy Session             |                |   |                  |                  | X                |                  | X                |                |                  | X                |                |
| 7 days Integrative Telephone Contact    |                |   |                  |                  | X I   |                  | X I   |                |                  | X I   |                |
| AEs Requiring Medical Attention         |                |   |                  | X                | X                | X                | X                | X              | X                | X                | X              |
| Spont. Reported Reactions and all AEs   |                |   |                  | X                | X                | X                | X                |                | X                | X                |                |
| Changes in Tinnitus and/or Pain         | X O |   | X E,O | X O | X E,O | X E,O | X O |
| AEs of psychiatric status or withdrawal |                | X | X                | X                | X                | X                | X                | X              | X                | X                | X              |
| Serious Adverse Events                  |                | X | X                | X                | X                | X                | X                | X              | X                | X                | X              |
| Issue Memory Aid Card H      |                |   |                  |                  |                  |                  |                  |                |                  |                  | X              |
| Unblinding J                 |                |   |                  |                  |                  |                  |                  | X              |                  |                  |                |
| Perception of Third Session             |                |   |                  |                  |                  |                  |                  | X N |                  |                  | X N |
| RRPQ                                    |                |   |                  |                  |                  |                  |                  |                |                  |                  | X H |

A =First Integrative session is 1 day after exp session B = At least 24 hrs prior to 1st exp. session C =Approximately 6 hours post MDMA D =At the beginning of the session E =As needed F=Approximately every 60 minutes G =Given on 2nd preparatory session after meds are tapered (V3) H = Only for subjects starting Long term Follow up and not going to Stage 2 I =For 7 days post Exp. Session, C-SSRS D2 and D7 of calls only, General well being for all 7 days J =Subjects in the medium or low dose group will not have visits 14-18, but will instead move onto Stage 2. K= On the day of the 1st integrative session following the Exp. Session L=CAPS may be videotaped M=First preparatory session (V2) may happen at the time of screening, before enrollment. N= Full dose subjects only. O= Only in subjects with pre-existing tinnitus and/or chronic pain.

| Table 4.1: Stage2 Time & Events            | Preparatory                        | Experimental Session 1 |                         | Experimental Session 2 |                         |                              | Experimental Session 3 |                         | Follow-Up                                 | Long Term Follow-Up                               |
|--|------------------------------------|------------------------|-------------------------|------------------------|-------------------------|------------------------------|------------------------|-------------------------|---|---|
|  |                                    | V19*                   | V20                     | V 21,22,23             | V24                     | V 25,26,27                   | V28                    | V29                     |   |   |
| Visit #                                    | Preparatory Session                | Experimental Session 1 | Integrative Sessions    | Experimental Session 2 | Integrative Sessions    | Secondary endpoint           | Experimental Session 3 | Integrative Sessions    | End of Stage 2 & Outcome                  | 1 Year Follow-up                                  |
| Type of Visit                              | Within maximum of 5 months of V13* | After V19              | Before V24 A | 3-5 weeks post V20     | Before V28 A | 1 month post V24, before V29 | 3-5 weeks post V24     | Before V33 A | May happen over > 1 day 2 months post V29 | Follow-Up & Outcome                               |
| Visit Timing or Study day or Window        |                                    |                        |                         |                        |                         |                              |                        |                         |   | May happen over > 1 day. One Year post V14 or V29 |
| Confirm Informed Consent                   | X                                  |                        |                         |                        |                         |                              |                        |                         |   |   |
| Confirm Inclusion/Exclusion                | X                                  |                        |                         |                        |                         |                              |                        |                         |   |   |
| Enrollment in Stage 2                      | X                                  |                        |                         |                        |                         |                              |                        |                         |   |   |
| Collect Concomitant Medication             | X                                  | X                      | X                       | X                      | X                       | X                            | X                      | X                       | X   | X   |
| Record to Audio/Video                      | X                                  | X                      | X                       | X                      | X                       | X H               | X                      | X                       | X H                            |   |
| General Well-Being                         | X                                  | X                      | X                       | X                      | X                       |                              | X                      | X                       | X   |   |
| Drug Screen                                |                                    | X                      |                         | X                      |                         |                              | X                      |                         |   |   |
| Pregnancy Screen (if applicable)           |                                    | X                      |                         | X                      |                         |                              | X                      |                         |   |   |
| CAPS, GAF, BDI-II, PTGI, PSQI, DES-II (IR) | Use V13*                           |                        |                         |                        |                         | X                            |                        |                         | X   | X   |
| NEO PI with Ind. Rater                     | Use V13*                           |                        |                         |                        |                         |                              |                        |                         | X   | X   |
| C-SSRS                                     | X                                  | X C, D, E   | X G          | X C, D, E   | X G          |                              | X C, D, E   | X G          | X   | X   |
| Administer IP Drug + Therapy, SOCQ         |                                    | X                      |                         | X                      |                         |                              | X                      |                         |   |   |
| Monitoring of BP, Heart rate and Temp.     |                                    | X                      |                         | X                      |                         |                              | X                      |                         |   |   |
| SUD  |                                    | X D, F      |                         | X D, F      |                         |                              | X D, F      |                         |   |   |
